It is planned to enroll a total of 20 subjects aged 18 to 45 years with a body weight of > 40 kg with active SLE-CL that is not controlled by current standard of care medications at tolerable dosages.

Cohort 1 will undergo intense PK-evaluations during the **Intense PK Period of Part A**.

As shown in the figure above, subjects move from Part A to Part B to Part C of the study, unless they are discontinued from the study (see rescue clause, Section 6.5).

It is anticipated that almost all subjects will be treated with stable background therapy with an antimalarial (hydroxychloroquine, rarely chloroquine), up to 80% are treated with corticosteroids (CS), and about 50% of the subjects will also be treated with a non-biological DMARD (mostly methotrexate, azathioprine and mycophenolate mofetil) for prior multiorgan involvement with SLE.

Screening period

Duration up to 4 weeks; however, subjects should have the TD1 visit as soon as possible after the eligibility for the study has been confirmed.

In the event that a laboratory result does not meet inclusion/exclusion criteria for the study, the lab work may be repeated once in the four week period prior to the baseline visit to establish eligibility for the study.

If the subject fails screening for the study, they may be re-screened one time after the screen failure with permission from the sponsor. Subject will retain the same subject number as assigned at the initial study visit.

If a patient discontinues before the baseline visit, only the demographic information and inclusion/exclusion criteria with the primary reason for discontinuation should be completed on the eCRF. It is not necessary to complete all the required evaluations at the time of discontinuation unless medically indicated.

Part A (TD1 – week 8)

The primary objective of Part A is to characterize the PK of TOFA at the 5mg dose based on Cohort 1 data. Standard of care (SOC) therapies are kept stable during Part A. All background medications, including CS remain unchanged.

Cohort 1

Intense PK Period: PK sampling will only be done for subjects in Cohort 1. Starting at TD1, subject will be monitored at least weekly. PK sampling will occur pre-dose on Day 5 (approximately 11-13 hours after the second dose on Day 4) and 0.5, 1, 2, 4 and 8 hours post first dose on Day 5.

Cohort 2

Only if ≥ 1 subject of the Cohort 1 patients has shown partial response of SLE-CL to TOFA by week 4, will **Cohort 2** be enrolled.

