6.5 Rescue clause, treatment failure & subject withdrawal

A subject will be considered a treatment failure and discontinued from the study if he/she experiences one or more of the following:

- Serious adverse event that is possibly related to TOFA;
- Important worsening of renal disease defined as a persistent increase in proteinuria as measured by the protein: creatinine (PC) ratio to values > 2.0 after achieving complete response of lupus nephritis, or doubling of proteinuria with values PC ratio > 3.0 after achieving a partial response of lupus nephritis;
- Need to increase current or initiation of new SLE background therapy due to non-renal SLE manifestations;
- Life-threatening SLE complications as judged by the investigator;
- Need for more than the protocol defined allowable CS rescue therapy as determined by the treating physician;
- No improvement of SLE-CL as measured by the CLASI by week 8;
- Two sequential absolute lymphocyte counts less than $< 0.5 \times 10^9$ or 500 cells/mm³;
- Two sequential hemoglobin values < 8.0 g/dL (80 g/L) or decreases greater than 2 g/dL on treatment;
- Female subjects that become pregnant during the study will discontinue study treatment. They will be continued to be followed in accordance as outlined in section **7.3.10**.

Subject Withdrawal

Subjects may withdraw from the study at any time at their own/their legal guardian's request, or they may be withdrawn at any time at the discretion of the physician investigators for safety, behavioral, or administrative reasons. If a subject does not return for a scheduled visit, every effort should be made to contact the subject. In any circumstance, every effort should be made to document subject outcome, if possible.

The investigator will inquire about the reason for withdrawal, request the subject to return all unused investigational product, request the subject to return for a final visit, if applicable, and follow-up with the subject regarding any unresolved AEs.

7 If the subject withdraws from the study, and also withdraws consent for disclosure of future information, no further evaluations should be performed, and no additional data should be collected. The sponsor may retain and continue to use any data collected before such withdrawal of consent. Planned Assessments & Evaluations

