8.3 Effectiveness Analyses

Due to the small sample size, results may not show statistical significance. Statistical significance may not be reached in final data analysis. However, a trend towards improved clinical status may assist planning efforts of a larger clinical trial to assess efficacy.

The efficacy population will be all subjects who were enrolled in the study and received at least 1 dose of TOFA. No interim analyses are planned. We will perform intention-to-treat analyses, with the last observation carried forward in primary analyses; and will also perform analyses on observed data in secondary analyses. As this is an open-label study, no control group is available. Efficacy measures are listed under Section 7. Data of subjects who enter Part B before week 8 and/or Part C before week 24 will be

considered on a last-observation (LOC) carried forward basis for endpoints of Part A and B, respectively.

To assess the benefits of TOFA on skin manifestations of SLE, we will use descriptive analysis and contingency table analysis, using Chi-square and Fisher Exact test as appropriate, to determine the proportion of subjects who are partial or complete CLASI responders at weeks 4, 8 and 24 compared to baseline. To assess the effect of TOFA on skin damage, we will compare the change (increase) of CLASI damage score¹⁶ from baseline to the end of Part B and C, respectively, using paired T-tests.

To assess the steroid –sparing properties of TOFA, we will determine the proportion of study subjects who can discontinue steroids at the end of Part B and C, respectively. We will also evaluate steroid sparing properties of TOFA for SLE-CL by comparing steroid doses (absolute and weight-adjusted) at baseline with those in the end of Part B and C, using a paired T-test.

Similarly, we will assess TOFA effect of overall disease activity in SLE as measured by the numeric SLEDAI and BILAG scores, respectively. We will also perform sub-analyses and evaluate improvement or resolution of other organ-system activity (e.g. serological activity – measured by anti-dsDNA antibodies and low complement levels; joint counts) using paired T-tests and contingency table analysis, as appropriate. In a similar fashion the change of the other SLE core response variables (CRV) besides disease activity (SLEDAI, BILAG) will be assessed at each study visit.

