 - Platelet count <100x 10⁹/L.
 - Lymphocyte count of <0.5 x 10⁹/L.
23. AST or ALT > 1.5 times the upper limit of normal or any other clinically significant laboratory abnormality.
24. History of any other rheumatic autoimmune disease.
25. Infections:
 - Latent or active TB or any history of previous TB.
 - Chronic infections.
 - Any infection requiring hospitalization, parenteral antimicrobial therapy or judged to be opportunistic by the investigator within the 6 months prior to the first dose of study drug.
 - Any treated infections within 2 weeks.
 - History of recurrent (more than one episode) herpes zoster or disseminated (a single episode) herpes zoster or disseminated (a single episode) herpes simplex.
 - History or current symptoms suggestive of any lymphoproliferative disorder, including Cytomegaly Virus (CMV) or Epstein Barr Virus (EBV) related lymphoproliferative disorder, history of lymphoma, leukemia, or signs and symptoms suggestive of current lymphatic disease.
26. Patients taking potent and moderate cytochrome P450 3A4 (CYP3A4) inhibitors.

27. Patients taking potent and moderate CYP3A4 inducers.
28. Patients who have been vaccinated with live or attenuated vaccines within the 6 weeks prior to the first dose of study medication. All study participants should be up-to-date with respect to standard of care vaccinations (as defined by their country health ministry) as permitted by past immunosuppressive therapy for SLE.
29. Patients with a malignancy or with a history of malignancy with the exception of adequately treated or excised non-metastatic basal cell or squamous cell cancer of the skin or cervical carcinoma in situ.
30. Subjects with a history or current diagnosis of diverticulitis.

D. SAMPLE SIZE

This is a 3-part study designed to evaluate the PK-PD of TOFA in subjects 18-45 years with at least moderately active SLE -CL. Safety and efficacy will be evaluated as secondary objectives. No formal sample size estimation was done but previous TOFA studies in other populations suggest that 20 subjects are sufficient to achieve the objectives of this study.

It is planned to enroll:

Cohorts 1: n=10, weight > 40 kg and age \geq 18 years up to and including age 45 years.

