16. Water bothers my skin condition (bathing, washing hands)					
17. My skin condition makes showing affection difficult					
18. I worry about side effects from skin medications/treatments					
19. My skin is irritated					
20. My skin condition affects my interactions with others					
21. I am embarrassed by my skin condition					
22. My skin condition is a problem for the people I love					
23. I am frustrated by my skin condition					
24. My skin is sensitive					
25. My skin condition affects my desire to be with people					
26. I am humiliated by my skin condition					
27. My skin condition bleeds					
28. I am annoyed by my skin condition					
29. My skin condition interferes with my sex life					
30. My skin condition makes me tired					

APPENDIX 5

Cutaneous LE Disease Area and Severity Index (CLASI)

Select the score in each anatomical location that describes the most severely affected cutaneous lupus-associated lesion

		activity	damage		
Anatomical Location	Erythema	Scale/ Hypertrophy	Dyspigmentation	Scarring/ Atrophy/ Panniculitis	Anatomical Location
	0-absent 1-pink; faint erythema 2- red; 3-dark red; purple/violaceous/ crusted/ hemorrhagic	0-absent; 1-scale 2-verrucous/ hypertrophic	0-absent, 1-dyspigmentation	0 – absent 1 – scarring 2 – severely atrophic scarring or panniculitis	
Scalp				See below	Scalp
Ears					Ears
Nose (incl. malar area)					Nose (incl. malar area)
Rest of the face					Rest of the face
V-area neck (frontal)					V-area neck (frontal)
Post. Neck &/or shoulders					Post. Neck &/or shoulders
Chest					Chest
Abdomen					Abdomen
Back, buttocks					Back, buttocks
Arms					Arms
Hands					Hands
Legs					Legs
Feet					Feet

Mucous membrane

Dyspigmentation

Mucous membrane lesions (examine if patient confirms involvement)	Report duration of dyspigmentation after active lesions have resolved (verbal report by patient – tick appropriate box)

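### Last-observation-carried-forward puts week-8 CLASI damage scores in place of week-24 and week-76 scores, and with 20 subjects and no control a non-significant paired t-test cannot show absence of damage (minor)

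*Combined protocol and SAP*

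**What the plan says.** Change in CLASI damage score is an exploratory endpoint for Parts B and C (Section 4.3). Section 8.3 gives the analysis: "we will compare the change (increase) of CLASI damage score" and then "from baseline to the end of Part B and C, respectively, using paired T-tests". The same section notes that there is no control group and sets the handling of missing data: "We will perform intention-to-treat analyses, with the last observation carried forward in primary analyses". Observed-data analyses are secondary.

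Three other provisions determine what LOCF does here.

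- Section 6.5 lists, among the reasons for discontinuing a subject, "No improvement of SLE-CL as measured by the CLASI by week 8". Section 7.1 plans only a telephone call 10 weeks after the last dose, with no further CLASI.
- Sections 4.3 and 8.3 apply LOCF to subjects who enter Part C before week 24, for the Part B endpoints. Section 3 keeps those same subjects on the Part B visit schedule until week 24.
- Appendix 5 defines the damage score as dyspigmentation plus scarring, atrophy or panniculitis (top category "2 – severely atrophic scarring or panniculitis") plus scalp scarring.

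On size, Section 3 says "It is planned to enroll a total of 20 subjects aged 18 to 45 years". Cohort 2 opens "Only if ≥ 1 subject of the Cohort 1 patients has shown partial response of SLE-CL to TOFA by week 4". Appendix 3, Section D states "No formal sample size estimation was done". For the damage test the documents give no alpha, sidedness, expected increase, SD or confidence interval.

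**The concern.** Two features of the planned test need attention.

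First, carry-forward suits this score poorly. Damage is a quantity expected to build up over time, and 8.3 itself glosses the change as an increase. A score taken at week 8 is not an estimate of the score at week 76. The subjects it is carried forward for are selected: they leave because the skin did not improve. For early movers to Part C the substitution is avoidable, because their week-24 score has been collected.

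Second, the null hypothesis is zero change and the hoped-for finding for damage is little or no increase. For steroid dose or SLEDAI, low power works against the drug. For damage, low power makes a non-significant result easier to obtain. A p-value alone therefore tells the reader little, and the plan specifies no interval to go with it.

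At stake is how well the trial describes damage on treatment, which a later and larger study might rely on.

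**Working it through.** **Plan's own figure.** The planned 20 subjects cannot be reproduced, because no calculation was made. The results below are in SD units of the change, since the documents give no SD.

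**Sample size under the primary analysis.** The efficacy population is everyone enrolled and dosed. With LOCF, exits stay in the analysis, so n is 20, or 10 if Cohort 2 never opens. Smaller numbers apply only to the secondary observed-data analysis.

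**Power of the paired t-test** (two-sided 5%, assumed). Noncentrality = d·√n, with n − 1 degrees of freedom.

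- n = 20, d = 0.5: 0.5 × √20 = 2.24, power 0.565, so the increase is missed 44% of the time. One-sided 5%: power 0.695, missed 31%.
- n = 20, other increases: power 0.136 at d = 0.2, 0.247 at d = 0.3 and 0.80 at d = 0.66.
- n = 10, d = 0.5: power 0.293, missed 71%.

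**Confidence interval.** Half-width = t(0.975, n − 1)/√n. At n = 20 this is 2.093/4.472 = 0.47 SD; at n = 10 it is 0.72 SD. A result that just fails significance at n = 20 has an observed mean just under 0.47 SD. Its upper limit is then almost 0.47 + 0.47 = 0.94 SD.

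**Effect of carrying week 8 forward.** Assume linear accrual, and that exits accrue at the same rate as the others. An exit at week 8 keeps 8/T of its change at week T: 8/24 = 33% at week 24 and 8/76 = 11% at week 76. If a fraction f exits, the mean is understated by f × (1 − 8/T). The exit fraction is not in the documents, so a range is shown.

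| f (assumed) | Week 24 | Week 76 |
|---|---|---|
| 20% | 0.2 × 0.667 = 13% | 0.2 × 0.895 = 18% |
| 30% | 0.3 × 0.667 = 20% | 0.3 × 0.895 = 27% |
| 40% | 0.4 × 0.667 = 27% | 0.4 × 0.895 = 36% |

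**Both together.** In a simulation of 40,000 trials (n = 20, true increase 0.66 SD at week 76), power falls from 80% with no exits to 61–72% with 20% exits and 40–61% with 40% exits. The lower end keeps the SD of the carried values constant; the upper end lets it shrink with the mean.

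**Early movers to Part C.** The footnote to Part C allows entry from week 8. Taken literally, the LOCF sentence could therefore put a score as old as week 8 in place of a week-24 score already in the database.

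**The case against.** The plan is more cautious than the test alone suggests. Section 8.3 opens by warning that significance may not be reached and presents the results as a possible trend to help plan a larger trial. A reader might infer that a non-significant result will be reported as no damage. No text says so; what is missing is an interval and a sentence to prevent that reading.

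A reader might also infer that a miss is the more likely outcome. At n = 20 and 0.5 SD it is 44%, below one half. Whether it is more likely than not depends on an increase, an SD and an exit rate that the documents do not give.

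The claim that carry-forward must hide damage is also too strong. Appendix 5 recognises dyspigmentation lasting under 12 months, so the score can fall and LOCF can freeze damage that would have cleared. Nor does any passage establish that week-8 exits accrue damage faster than others; it is plausible only.

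The planned observed-data analysis does not carry week-8 values forward and could use the real week-24 scores of early movers. That stands in part. It is secondary, and with no CLASI after exit it rests on those who stayed. If 40% left, n would be 12 and a 0.5-SD increase would be missed 65% of the time.

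Finally, the endpoint is one of many exploratory ones in a study whose primary objectives are PK and safety. That stands and limits the weight of the point.

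**Conclusion.** The point holds as a minor one. Followed as written, the primary analysis uses week-8 damage scores as week-24 and week-76 scores for non-improvers, and may discard collected week-24 scores for early movers to Part C. With linear accrual and 20–40% week-8 exits, both assumed, the mean increase is understated by 13–27% at week 24 and 18–36% at week 76. The direction is likely rather than certain.

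Separately, with at most 20 subjects and no control, a non-significant result cannot show that damage did not accrue: a 0.5-SD increase is missed 44% of the time (two-sided 5%, assumed), and the interval extends 0.47 SD either side of the estimate. These two figures do not depend on the accrual or exit assumptions.

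The documents do not support the stronger conclusion that the plan will declare absence of damage, or that it is set up to do so.

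**What to change.** In Section 8.3, for CLASI damage only:

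1. Make the primary analysis a mixed model of the damage score on weeks since TD1, using every observed CLASI visit, with a random intercept and a random slope if the model converges (random intercept only if not).
2. Use the actual week-24 scores of subjects who entered Part C early, and exempt this endpoint from the early roll-over LOCF sentence in Sections 4.3 and 8.3.
3. Report the estimated change with its 95% CI at weeks 24 and 76.
4. State that a non-significant change is not evidence of no damage.
5. Keep LOCF as a sensitivity analysis.

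No margin is needed: the documents offer no basis for one, and the aim is to estimate the change.

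The cost is SAP wording and one model. Section 10 schedules the CLASI at every visit, and the Appendix 5 form scores damage alongside activity, so no new data are required provided the damage half is completed each time. The downside is that the model assumes missing at random and linear accrual. It cannot recover damage that nobody observed after exit, and with 20 subjects the interval may be wide.

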Cohort 2 subjects will be seen in weekly intervals during Part A.

Cohort 1 and 2 subjects with clinical remission of SLE-CL can enter Part B as early as week 4 post baseline. Subjects who move from Part A to Part B prior to Week 8, will still be evaluated using the same visit schedule as subjects remaining in Part A until week 8.

Part B (week 8* – 24)

The primary objective of Part B is to assess safety and tolerability of TOFA, secondary objectives include effectiveness. Specifically, the PK of TOFA at the 5 mg dose based on Cohort 1 will be characterized.

- If CS are primarily given for SLE-CL, then CS may be decreased for clinically significant improvement as defined by a *Cutaneous Lupus Erythematosus Disease Area and Severity Index (CLASI)* activity score by $\geq 50\%$ from baseline and must be tapered for CLASI activity scores of 0 for > 2 months.

* Roll-over subjects in SLE-CL clinical remission may enter Part B as early as week 4

- If CS are mainly prescribed for other SLE manifestations besides SLE-CL, then CS can be decreased as per the investigator's decision, based on clinically significant findings of improvement.
- If the subject has been discontinued from CS and continues to be in SLE-CL clinical remission (CLASI activity score = 0), then the subject can enter Part C.

Subjects who move from Parts B to Part C prior to Week 24 will still be seen using the same visit schedule as subjects remaining in Part B until week 24.

Part C (week 24[†] – 76)

During Part C all therapies can be altered, per investigator discretion, with the exception of TOFA. The TOFA dose will remain stable throughout the study. Subjects who exit Part A or B early due to SLE-CL improvement will remain in Part C until they have been in the study for a total of 76 weeks.

4. Study description

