4.2 Key Secondary Objective(s) & Endpoint(s)

Secondary objectives

- To evaluate the efficacy of TOFA with SLE-CL over time compared to baseline

Secondary endpoint

Part A and B:

- Proportion of subjects that achieve a skin response (complete or partial response) as per the validated (CLASI) at weeks 4, 8 and 24 compared to baseline at TD1¹⁴. Response is defined as follows:
 - *Complete response (CR)* : complete resolution of the inflammatory rash (CLASI activity score = 0);
 - *Partial response (PR)*: $\geq 20\%$ improvement of the CLASI activity score. A partial response (PR) is considered clinically significant
 - *No response*: $< 20\%$ improvement or even worsening of the CLASI activity score
 - *Cutaneous relapse*: a new CLASI activity score ≥ 4 in those subjects who previously achieved CR of SLE-CL (CLASI=0)

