4.3 Exploratory Objective(s) & Endpoint(s)

Exploratory objectives

Part A:

- To evaluate single cell expression patterns of skin biopsies of affected and non-affected skin with TOFA therapy
- To examine changes in interferon α/γ receptor, STAT phosphorylation patterns with TOFA therapy using immunohistochemistry
- To investigate mRNA expression patterns in peripheral blood upon treatment with TOFA with focus on interferon regulated genes

Parts B and C:

- To evaluate steroid sparing properties of TOFA for SLE-CL
- To evaluate TOFA effect of overall disease activity in SLE as measured by the SLEDAI and BILAG
- To evaluate effects of TOFA on quality of life as measured by the Skindex (appendix 4) and overall well-being

Exploratory endpoints at week 4, 8, 12, 24, 52, and 76

Part A: Pharmacodynamics (PD)

- PD parameters include assessment of inhibitory effect of TOFA on expression of IL-2 responsive target genes downstream of the JAK/STAT pathway, such as FOXP3, SOCS3, IL-2R α , interferon - γ and granzyme B.

Parts B and C:

- Decrease of absolute dose of systemic CS from baseline
- Decrease of body weight adjusted CS dose from baseline
 - CS dosing is measured in prednisone-equivalents
- Proportion of subjects who discontinue systemic CS
- Proportion of subjects with cutaneous relapse
- Change of BILAG score from baseline¹³
- Absolute value and percent change in plasma: Complement C3 and C4d, autoantibodies (anti-dsDNA)
- Change in number of inflamed joints from baseline¹⁴
- Change in SKINDEX score from baseline¹⁵
- Change of CLASI damage score¹⁶ from baseline
- Change in SLEDAI score at each time point
- Change in protein: creatinine ratio at each time point.
- Change in subject's overall well-being at each time point
- Change in subject's ESR
- Proportion of subjects with clinically important reduction in SLE activity at each time point, based on CRV changes compared to baseline
- Proportion of subjects with flare of SLE activity at each time point, as defined by the BILAG¹⁷

Data of subjects who enter Part B before week 8 and/or Part C before week 24 will be considered on a last-observation (LOC) carried forward basis for endpoints of Part A and B, respectively.

5. Study Participants

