This 76-week, 3-part, Phase 1b/2 study is intended to evaluate the pharmacological properties (pharmacokinetics and pharmacodynamics) of TOFA administrated to young adults with moderately to severely active inflammatory *SLE-CL*.

- **Part A** (up to week 8) requires stable background medications;
- **Part B** (up to week 24) allows for tapering of *corticosteroids (CS)*, *in the setting of significant clinical improvement of SLE-CL as defined by a decrease in Cutaneous Lupus Erythematosus Disease Area and Severity Index (CLASI) activity score by ≥50% from baseline*, and

Part C (until week 76) permits tapering of other background medications in subjects with clinical remission of SLE-CL (CLASI activity score=0). TOFA dosing is kept stable during Part C.

Primary Objective

Part A (Cohort 1):

- To evaluate the pharmacokinetic (PK) profiles of TOFA in young adults aged between 18 and including 45 years with SLE -CL who are on stable treatment for SLE

Part A (Cohort 1 and Cohort 2)

- To evaluate the safety and tolerability of TOFA in young adults with SLE -CL

Part B and C:

- To evaluate the safety and tolerability of TOFA in young adults with SLE -CL

Primary endpoints

Part A (Cohort 1 only):

- **Day 5:** AUC_{inf} and C_{max} of tofacitinib

Part B: At Week 24

- Nature, severity, and frequency of adverse events
- Incidence and severity of laboratory abnormalities

Key Secondary Objective(s) & Endpoint(s)

Secondary objectives

- To evaluate the efficacy of TOFA in young adults with SLE -CL

Secondary endpoint**Part A and B****Efficacy on SLE skin disease**

- Proportion of subjects who achieve a skin response (complete or partial response) as per the validated Cutaneous Lupus Erythematosus Disease Area and Severity Index (CLASI) at weeks 4, 8 and 24 compared to baseline¹⁶. Response (compared to baseline at TD1) is defined as follows:
 - *Complete response (CR)* : complete resolution of the inflammatory rash (CLASI activity score = 0);
 - *Partial response (PR)*: $\geq 20\%$ improvement of the CLASI activity score
 - *No response*: $< 20\%$ improvement or even worsening of the CLASI activity score (CLASI relapse)

Exploratory Objective(s) & Endpoint(s)**Exploratory objectives****Part A:**

- To evaluate single cell expression patterns of skin biopsies of affected and non-affected skin with TOFA therapy
- To examine changes in interferon α/γ receptor, STAT phosphorylation patterns with TOFA therapy using immunohistochemistry

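### Steroid-sparing endpoints ignore skin state at the same visit, and CLASI response is not analysed after week 24, so skin control lost by tapered partial responders can go uncounted

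*Combined protocol and SAP*

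**What the plan says.** **Objective.** Section 4.3 sets, for Parts B and C, "To evaluate steroid sparing properties of TOFA for SLE-CL".

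**When CS may be reduced.** Section 3 (Part B) says "If CS are primarily given for SLE-CL, then CS may be decreased for clinically significant improvement as defined by a" fall of at least 50% in the CLASI activity score. Sections 2, 6 and 6.2 use the same threshold, as does Appendix 3 section B: "Disease Area and Severity Index (CLASI) activity score by ≥50% from baseline".

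**How steroid sparing is judged.** Section 8.3 plans "comparing steroid doses (absolute and weight-adjusted) at baseline with those in the end of Part B and C, using a paired T-test", and the proportion who stop steroids by the end of Part B and of Part C. Section 4.3 lists the same quantities. No minimum reduction and no skin condition is attached.

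**How skin outcome is judged.** Section 4.2 defines partial response (PR) as at least 20% improvement in CLASI activity. Sections 4.2 and 8.3 analyse response at weeks 4, 8 and 24 only. Cutaneous relapse is "a new CLASI activity score ≥ 4 in those subjects who previously achieved CR of SLE-CL (CLASI=0". The related endpoint in section 4.3 is "Proportion of subjects with cutaneous relapse", with no denominator given.

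**A second use of the word.** Appendix 3 section B describes its No response category as less than 20% "improvement or even worsening of the CLASI activity score (CLASI relapse", with no requirement for an earlier CLASI of 0. The endpoint list later in the same section does require an earlier complete response (CR).

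**The concern.** Steroid sparing for a skin indication means that the dose comes down while the skin stays controlled. The plan measures the first half of that and does not join it to the second. The protocol itself permits the reduction at 50% improvement, and requires it after sustained CLASI 0, so in a single-arm study a lower dose is partly an instruction carried out. What would distinguish success from failure is the state of the skin afterwards.

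The one endpoint aimed at skin worsening, cutaneous relapse, cannot apply to a subject who tapered at 50% to 99% improvement and never reached 0. Section 8.3 says that a trend may help to plan a larger efficacy trial. A steroid-sparing trend that takes no account of skin outcome would be a poor basis for that.

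**Working it through.** The plan has no figure to reproduce: Appendix 3 section D states that no formal sample size estimation was done. The check is threshold arithmetic on integer CLASI scores, then an illustration of the dose test.

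**1. Week 24.** Let B be baseline CLASI activity, at least 8 by inclusion criterion 4. Taper is permitted at scores up to 0.5 × B. PR is kept at scores up to 0.8 × B. Relapse needs an earlier 0. For a subject who tapers at exactly 50% improvement and never reaches 0:

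| Baseline | Taper at | Highest score still PR | No response from | Uncounted band |
|---|---|---|---|---|
| 8 | 4 | 6 (0.8 × 8 = 6.4) | 7 | 5–6 |
| 20 | 10 | 16 | 17 | 11–16 |
| 40 | 20 | 32 | 33 | 21–32 |

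The share of the gain that can be lost while PR is kept is at most (0.50 − 0.20) / 0.50 = 60%. For a taper begun at 90% improvement it is (0.90 − 0.20) / 0.90 = 78%. Throughout the band the subject is a responder, is not a relapse and contributes a lower dose.

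Contrast a complete responder with baseline 8 who goes from 0 to 4. That is a relapse, yet a score of 4 from baseline 8 is also the 50% improvement that permits a taper in someone who never reached 0.

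**2. After week 24.** Take baseline 20, CS reduced at a score of 10, CS stopped, and CLASI 20 at week 76:

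- dose change at the end of Part C: a reduction;
- off CS at the end of Part C: yes;
- cutaneous relapse: cannot occur, because there was no earlier 0;
- CLASI response: not analysed after week 24.

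The only other CLASI endpoint running to week 76 is the damage score.

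**3. The dose test.** Section 3 expects up to 80% on CS at entry, so 0.80 × 20 = 16 users. Assume, for illustration, that k of the 16 reduce by 2.5 mg/day and the rest do not change. For k = 4:

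- mean difference = 4 × 2.5 / 16 = 0.625;
- SD = √[(4 × 2.5² − 16 × 0.625²) / 15] = √1.25 = 1.118;
- t = 0.625 / (1.118 / √16) = 2.24 on 15 degrees of freedom, p = 0.041.

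For k = 5, 6 and 8, p = 0.020, 0.0090 and 0.0015. Adding 4 non-users with zero change (n = 20) gives 0.042 for k = 4 and 0.0021 for k = 8. CLASI does not enter the calculation, so these values are the same whether the skin stayed clear or returned to baseline.

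**The case against.** The strongest reply is that the plan is far from blind to returning skin disease.

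- CLASI is scheduled at every visit, and section 7.1.1 lists it as an activity measure. The data will exist.
- A reader might infer that a subject with CLASI 16 at baseline, 8 at taper and 16 again at week 24 is scored a full success. The documents do not support this. That is 0% improvement, hence No response on the week-24 secondary endpoint, which ranks above the exploratory steroid endpoints.
- A reader might also infer that later loss of response has no consequence. Section 6.5 makes a need to increase or start background therapy for non-renal SLE a treatment failure. Its reach in Part C is less clear, because section 3 lets therapies other than TOFA change there.
- BILAG-defined flare and changes in SLEDAI, BILAG and Skindex (section 4.3) need no earlier CLASI 0. Section 7.3.3 gives worsening of the underlying disease as an example of an adverse event.
- A taper reversed before the end of Part B or C does not count as a reduction in the section 8.3 test.

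All of this stands, and it rules out calling the worsening invisible. It does not close the gap. Treatment failure is not a listed endpoint. None of the other measures is tied to the taper or specific to CLASI activity. Appendix 3 section B bases flare on core response variables that do not include CLASI, unlike the BILAG definition in section 4.3. The 50–80% band at week 24, and any loss in a partial responder after week 24, remain outside every CLASI activity endpoint.

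**Conclusion.** The point holds in a bounded form. At week 24 the gap is the band above 50% and up to 80% of baseline CLASI, equal to as much as 60% of the gain in a subject who tapers at exactly 50% improvement. Scores above 80% of baseline are reported as No response. From week 24 to week 76 the gap covers any loss of response in a subject who never reached CLASI 0, although steroid sparing is tested at week 76.

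Each such subject who is off CS moves the discontinuation proportion by 1/20 = 5 points if all treated subjects are the denominator, or 1/16 = 6.25 points if only the expected 16 CS users are. Section 8.3 does not settle which. The p-values above rest on assumed doses and show only that the test is indifferent to skin state. How many subjects would follow this course cannot be derived from the documents.

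It would go too far to say that the trial cannot address steroid sparing. The needed data are collected, and what is missing is a prespecified link between dose and skin. The affected endpoints are exploratory, in an uncontrolled study of 20. The primary PK and safety results are untouched.

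**What to change.** Leave the taper rules as they are. In sections 4.3 and 8.3 and in Appendix 3:

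1. **Joint summary.** At the end of Part B and of Part C, report the proportion with CS reduced or stopped and skin response maintained at the same visit, with dose change alone as supportive. Show it at the existing PR threshold and again at the 50% improvement that permitted the taper, because the 20% cut-off alone misses the band above. State the denominator. Where the last observation is carried forward, take dose and CLASI from the same visit.
2. **Longer skin follow-up.** Extend the CLASI response summary to weeks 52 and 76, which section 4.3 already names as exploratory time points. Section 7.1 puts Part C visits every 8 weeks, and counting from week 24 gives weeks 48 and 56, so say which visit serves as week 52. Add loss of skin response for everyone who earlier reached PR or CR, overall and among those who tapered.
3. **One meaning of relapse.** Reconcile the No response label in Appendix 3 section B with the definition in section 4.2 and the endpoint list in that appendix, and state the relapse denominator.

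Optionally, state that baseline weight is used for the weight-adjusted dose. Appendix 3 section L lists weight gain as a common effect. An assumed gain of 2%, 5% or 10% would lower mg/kg by 1 − 1/1.02 = 2.0%, 1 − 1/1.05 = 4.8% or 1 − 1/1.10 = 9.1% with no change in dose taken.

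Cost: a small protocol wording change in section 4.3 plus analysis text. CLASI, weight and concomitant medication are already scheduled, so no new data are needed. The reported steroid-sparing rate may be lower.
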